2.4 Goal 4 mRNA

Explore whether mRNA gene expression before and after scrambler therapy shows similar findings to what Starkweather et al observed.

Hypothesis 4: Scrambler therapy will be associated with mRNA gene expression modifications as was previously reported by Starkweather et al.

2.5 Goal 5 fMRI

Utilizing high-field MRI, to define alterations in functional differences (using resting state BOLD measures to measure differences in functional connectivity) in treated with the Scrambler device in the setting of chemotherapy induced peripheral neuropathy pain. In the same subjects, we will utilize high-field MRI to measure morphometric changes in specific cortical (cingulate, S1 and hippocampus) and subcortical regions (basal ganglia).

Hypothesis 5: Scrambler therapy will be associated with fMRI changes

2.6 Goal 6 Quantitative Sensory Testing

Explore whether Scrambler therapy will alter sensation.

Hypothesis 6: Scrambler therapy will be associated with improved sensation, as detected by quantitative sensory testing.

3.0 Patient Eligibility

3.1 Inclusion criteria

- 3.11 Age \geq 18 years.
- 3.12 Pain or symptoms of CIPN of \geq 3 months duration, for which the patient wants intervention.
NOTE: Neurotoxic chemotherapy must have been completed \geq 3 months prior to registration and there must be no further planned neurotoxic chemotherapy for $>$ 5 months after registration.
- 3.13 Patients have to relate that tingling or pain was at least a four out of ten problem \leq 7 days prior to registration, on a 0-10 scale where zero was no problem and ten was the worst possible problem.
NOTE: The patient is expected to have tingling or pain of at least 4/10 at the time of the first treatment (Appendix II: A or B).
- 3.14 ECOG Performance Status (PS) = 0, 1, or 2.

ECOG Performance Status*	
	ECOG Performance Status
0	Normal activity. Fully active, able to carry on all pre-disease performance without restriction.
1	Symptoms, but ambulatory. Restricted in physically strenuous activity, but ambulatory and able to carry out work of a light or sedentary nature (e.g., light housework, office work).
2	In bed $<$ 50% of the time. Ambulatory and capable of all self-care, but unable to carry out any work activities. Up and about more than 50% of waking hours.
3	In bed $>$ 50% of the time. Capable of only limited self-care, confined to bed or chair more than 50% of waking hours.
4	100% bedridden. Completely disabled. Cannot carry on any self-care. Totally confined to bed or chair.

*As published in Am. J. Clin. Oncol.:

- 3.15 Life expectancy \geq 6 months.
- 3.16 Ability to complete questionnaire(s) by themselves or with assistance.
- 3.17 Ability to provide informed written consent.
- 3.18 Case review by the study chair, or designate, as a case where treatment should be tried.
- #### 3.2 Exclusion Criteria
- 3.21 Any of the following because this study involves an investigational device whose genotoxic, mutagenic and teratogenic effects on the developing fetus and newborn are unknown:
- Pregnant women
 - Nursing women
 - Women of childbearing potential who are unwilling to employ adequate contraception
- 3.22 Existing operational implantable drug delivery systems, e.g. Medtronic

Synchromed.

- 3.23 Existing implantable medical electronic devices, life-supporting medical devices, and medical monitoring devices.
Note: Metal implants for orthopedic repair, e.g. pins, clips, plates, cages, joint replacements are allowed, as are central venous access devices.
- 3.24 History of myocardial infarction or ischemic heart disease within the past six months.
- 3.25 History of epilepsy, brain damage, use of anticonvulsants for seizure prevention, concurrently using ketamine, symptomatic brain metastases.
- 3.26 Skin conditions such as open sores that would prevent proper application of the electrodes.
- 3.27 Other medical or other condition(s) that in the opinion of the investigators might compromise the objectives of the study.
- 3.28 Currently receiving gabapentin or pregabalin and not willing to be weaned off of these medications prior to Scrambler therapy initiation.
Note: It is OK to continue these medications in patients who are receiving TENS. (See [Appendix I](#)).
- 3.29a History of peripheral neuropathy prior to receiving neurotoxic chemotherapy.
- 3.29b Prior treatment with Scrambler therapy.

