4.0 Test Schedule

Use for first treatment period; repeat for second treatment period

Tests and procedures	Active Monitoring Phase				
	≤30 days prior to registration	Day 1, Prior to therapy	Daily for 14 consecutive days beginning on Day 1 of active therapy	Last day of assigned therapy (±1 day)	Weekly for 8 weeks
History and exam, PS ¹ , Eligibility questions ² (Appendix II: A or B)	X				
Pregnancy test ³		X			
Declaration of most problematic site (upper versus lower extremities) and most problematic symptom (tingling versus pain): Appendix III	X				
Pain/tingling questionnaire regarding the prior week (Appendix IV: A or B)		X ⁴			
Patient Questionnaire: Before each treatment (Appendix V: A or B)		X ⁵	X ⁵		
Patient Questionnaire: After each treatment (Appendix VI: A or B)			X ⁵		
EORTC CIPN 20 (Appendix VII)		X		X ⁶	X
Patient Questionnaire: Analgesic Use (Appendix VIII)		X	X		X
Patient Questionnaire After each therapy and during weekly follow-up: Global Impression of Change and Patient Preference (Appendix IX: A or B)			X ⁷		X ⁷
Daily Treatment Log and Adverse Assessment (Appendix X)			X		
Individual Patient Dermatome Map-Electrode Placement (Appendix XI) Scrambler only			X		
Audiovisual recordings ^R			X ⁸		
Weekly follow-up patient questionnaire (Appendix XII:A or B)					X ⁹
Written patient summary (if the patient is willing to provide) ^R					X ¹⁰
Research Blood draw for CBC/diff and mRNA ^{11,R}		X		X	
fMRI ^{12,R}		X		X	
Quantitative Sensory Testing ^{13,R}		X		X	

Tests and procedures	Active Monitoring Phase				
	≤30 days prior to registration	Day 1, Prior to therapy	Daily for 14 consecutive days beginning on Day 1 of active therapy	Last day of assigned therapy (±1 day)	Weekly for 8 weeks
Study Coordinator/Nurse phone call to discuss therapy and any concerns, record any adverse events that are reported and to remind the patient to complete questionnaires and mail them			X ¹⁴		X

Footnotes:

1. PS must be done ≤7 days prior to registration.
 2. Appendix II A or B, as labeled depending on neuropathy area type. (This evaluation is used for eligibility.)
 3. For women of childbearing potential only. Must be done prior to first Scrambler therapy (or the first day of the second treatment period, if Scrambler therapy is crossover).
NOTE: This testing is not needed for TENS therapy.
 4. Appendix IV A or B, as labeled depending on neuropathy area to be treated

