6.5 Start of treatment

Treatment cannot begin prior to registration and must begin ≤ 50 days after registration.

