16.3 Analysis Plan**16.31 Primary endpoint**

Evaluate the efficacy of Scrambler therapy compared to TENS therapy for pain and/or tingling related to CIPN.

The main efficacy endpoint is defined as achieving 50% reduction in pain or tingling from baseline. At enrollment, patients will be asked to select either pain or tingling as their primary symptom of concern. Allowing the patients to select their main symptom (pain or tingling) is reasonable since the scores and the patterns of reduction were similar for pain and tingling after Scrambler therapy as shown by Pachman et al. (Pachman, Weisbrod et al. 2014)

Descriptive statistics (mean, sd, median, range) of pain and tingling scores and changes pre- and post-treatment scores will be summarized and the percentage of pain and tingling reduction from baseline will be calculated for each timepoint, separately by treatment arm. Longitudinal plots of scores by arm will be provided. The frequency and percentages of patients who achieved more than 50% reduction in pain and/or tingling scores after 2 weeks of therapy (scores from the last treatment day compared to the pre-treatment data, using the question related to average symptom [pain or tingling, whichever the patient chose when entering the study] over the previous 24 hours) and after 8 weeks of observation (scores from Week 8 form) from baseline (scores from Day 1 pre-treatment form) will be summarized by treatment arm and will be compared between arms using a Chi-square test (or Fisher-exact test as appropriate).

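### The 4/10 entry floor is not tied to the declared symptom or to the item used for the endpoint, so the 50% reduction can be computed from a very low or zero Day 1 baseline

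*Combined protocol and SAP*

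**What the plan says.** **Entry floor.** Section 3.13 accepts a patient if "tingling or pain was at least a four out of ten problem" in the 7 days before registration. The form used (Appendix II) asks how much of a problem each symptom has been over the past week. Nothing links the qualifying symptom to the one declared as primary.

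**First treatment.** The note to 3.13 adds: "The patient is expected to have tingling or pain of at least 4/10 at the time of the first treatment". This again covers either symptom, and no action follows if it is not met. The note points to Appendix II, but the Section 4.0 schedule has Appendices IV and V, not II, on Day 1.

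**Declared symptom.** Under 16.31, "patients will be asked to select either pain or tingling as their primary symptom of concern". Appendix III records it as the most problematic symptom.

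**Endpoint.** Section 16.31 compares the last treatment day with the Day 1 pre-treatment form, using the 24-hour-average question for the symptom, "whichever the patient chose when entering the study". Section 16.1 sets the threshold at a reduction of at least 50%; the analysis text in 16.31 says more than 50%.

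**Timing.** Section 4.0 lists Appendices II and III in the column headed "≤30 days prior to registration". Its footnotes shorten that window for performance status only: "PS must be done ≤7 days prior to registration". Under Section 6.5, treatment "must begin ≤ 50 days after registration".

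**The concern.** A percent-reduction responder endpoint needs a floor on the score that forms its denominator. Here the floor sits on a different quantity: either symptom rather than the declared one, a past-week problem rating rather than a 24-hour average, and a screening date that may precede Day 1 by weeks. The text therefore allows a patient to enter the primary analysis with a baseline of 0, 1 or 2.

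From 0 the outcome cannot be computed, and the plan does not say whether such a patient is a non-responder, missing or excluded. From 1 or 2, ordinary fluctuation can produce a response in either arm and dilute the difference. With 25 patients per arm, one or two such outcomes count. Section 16.5 says that p < 0.05 on the primary endpoint will be read as evidence that one therapy is better, and Section 16.6 does not replace patients whose primary endpoint data are missing.

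**Working it through.** **1. Longest gap from eligibility rating to baseline.** Under 3.13 (7 days) and 6.5 (50 days): 7 + 50 = 57 days. If the schedule column governed: 30 + 50 = 80 days.

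**2. Points needed to respond** on the integer 0–10 scale from baseline b. At least 50% needs ceil(b/2); more than 50% needs floor(b/2) + 1.

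| Baseline | At least 50% (16.1) | More than 50% (16.31) |
|---|---|---|
| 0 | undefined | undefined |
| 1 | 1 | 1 |
| 2 | 1 | 2 |
| 3 | 2 | 2 |
| 4 | 2 | 3 |
| 5 | 3 | 3 |
| 6 | 3 | 4 |
| 8 | 4 | 5 |

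The two thresholds differ at every even baseline.

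**3. Chance response.** Assume no true change and a normal change score with SD 1.5 or 2.0 (an assumption; the documents give no SD). For a required drop d, P = 1 − Φ((d − 0.5)/SD).

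| Required drop d | SD 1.5 | SD 2.0 | Baselines, at least 50% | Baselines, more than 50% |
|---|---|---|---|---|
| 1 | 36.9% | 40.1% | 1–2 | 1 |
| 2 | 15.9% | 22.7% | 3–4 | 2–3 |
| 3 | 4.8% | 10.6% | 5–6 | 4–5 |
| 4 | 1.0% | 4.0% | 7–8 | 6–7 |

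**4. Extra chance responders per arm**, assuming two patients per arm have baselines of 1–2 and the threshold is at least 50%:
- compared with baseline 4: 2 × (0.369 − 0.159) = 0.42 at SD 1.5; 2 × (0.401 − 0.227) = 0.35 at SD 2.0;
- compared with baseline 8: 2 × (0.369 − 0.010) = 0.72 at SD 1.5; 2 × (0.401 − 0.040) = 0.72 at SD 2.0.

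The excess is about 0.4 to 0.7, below one.

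**5. The plan's own power.** Table 16.51 (25 per arm, one-sided 0.05) reproduces with the pooled-variance normal approximation: power = Φ{[(p2 − p1)√n − 1.645√(2p̄(1 − p̄))] / √[p1(1 − p1) + p2(1 − p2)]}. For 0.20 versus 0.54: (1.700 − 1.123)/0.639 = 0.903, giving 81.7%. The five rows give 80.7, 80.4, 81.7, 81.3 and 82.1%, against the stated 80, 80, 81, 81 and 82%. Nothing in that table is in dispute here.

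**6. Illustrative effect on power**, with a fraction f of each arm affected (f is assumed). Response rates become p(1 − f) + f·r, where r is the chance-response rate.
- Two of 25 (f = 0.08) at baselines 1–2, r = 0.385 (mid-range): 0.20 becomes 0.184 + 0.031 = 0.215 and 0.54 becomes 0.497 + 0.031 = 0.528, giving 75.2%. Across the five rows: 72–75%.
- Two of 25 at baseline 0 counted as non-responders (r = 0): 75–77%.
- f = 0: unchanged at 80–82%.

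**The case against.** The strongest reply is that the gap is mostly theoretical. Appendix III records the most problematic symptom, and Appendix II rates how much of a problem each one is. A patient with pain at 5 and tingling at 0 who declares tingling would be contradicting himself. Criterion 3.18 adds case review by the study chair. Randomisation spreads low baselines over both arms, the declared symptom is a stratification factor (5.4), the trial is sized by feasibility and is not confirmatory (16.5), and 16.31 also summarises scores and changes, which do not share the percent-change problem. Much of this stands: a low declared score at screening is unlikely, and the expected harm is noise rather than bias. It does not cover a different item scored weeks later, and it gives no outcome to a patient whose baseline is 0.

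Four stronger readings go further than the documents allow.
- A reader of Section 4.0 might infer that a 30-day-old rating qualifies. Section 3.13 itself limits it to "7 days prior to registration, on a 0-10 scale where zero was no problem", preceded by a less-than-or-equal sign, and Section 13.1 makes a patient who fails any criterion ineligible. The two windows are an inconsistency to reconcile.
- A reader might infer that a patient below 4/10 on Day 1 cannot be removed. Section 13.3 allows cancellation for any reason before study treatment. That removal would come after the arm is assigned, so it does not replace a floor applied before randomisation.
- A reader might count two low-baseline patients per arm as about one extra responder. That counts all their chance responses (2 × 0.37 to 0.40 = 0.74 to 0.80), not the excess over higher baselines.
- A reader might take the power figures as an established loss. They depend on a frequency that the documents do not give. Under more than 50%, a baseline of 2 also needs two points, which lowers its chance response to 16–23%.

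**Conclusion.** The concern holds in a limited form. The entry floor and the endpoint baseline differ in symptom, question and date, and the plan has neither a minimum Day 1 score nor a zero-baseline rule. A very low or zero baseline is therefore permitted, though unlikely at screening.

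The undefined outcome at zero and the one-point response at a baseline of 1 (and of 2 under at least 50%) follow from the scale alone. The size of the harm does not: about 0.4 to 0.7 extra chance responders per arm, and power of roughly 72–77% in place of 80–82%, rest on an assumed SD of 1.5 to 2.0 and an assumed two affected patients per arm. If no such patients enrol, nothing is lost. This is worth correcting because it is cheap and the comparison is small, not because the trial is invalid without it.

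**What to change.** 1. **Section 3.13.** Require at least 4/10 for the symptom declared on Appendix III, scored before randomisation on the 24-hour-average item that the endpoint uses.
2. **Section 16.31.** State that a randomised patient with a Day 1 baseline of 0 stays in the denominator as a non-responder. Add a sensitivity analysis limited to Day 1 declared-symptom baselines of at least 4. This rule is needed as well as the first, because a floor before randomisation cannot guarantee a Day 1 score taken up to 50 days after registration. The restricted analysis selects on a score taken after assignment, so it should remain a sensitivity analysis.
3. **Consistency.** Reconcile the 7-day window in 3.13 with the 30-day column for Appendix II in Section 4.0, and the at-least-50% threshold in 16.1 with the more-than-50% threshold in 16.31.

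Cost: one reworded criterion, the 24-hour-average item added at screening, one schedule footnote, and a few sentences in the analysis plan. The downside is that a few patients with a low declared symptom would be screened out or would declare the other symptom.

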4.0 Test Schedule

Use for first treatment period; repeat for second treatment period

Tests and procedures	Active Monitoring Phase				
	≤30 days prior to registration	Day 1, Prior to therapy	Daily for 14 consecutive days beginning on Day 1 of active therapy	Last day of assigned therapy (±1 day)	Weekly for 8 weeks
History and exam, PS ¹ , Eligibility questions ² (Appendix II: A or B)	X				
Pregnancy test ³		X			
Declaration of most problematic site (upper versus lower extremities) and most problematic symptom (tingling versus pain): Appendix III	X				
Pain/tingling questionnaire regarding the prior week (Appendix IV: A or B)		X ⁴			
Patient Questionnaire: Before each treatment (Appendix V: A or B)		X ⁵	X ⁵		
Patient Questionnaire: After each treatment (Appendix VI: A or B)			X ⁵		
EORTC CIPN 20 (Appendix VII)		X		X ⁶	X
Patient Questionnaire: Analgesic Use (Appendix VIII)		X	X		X
Patient Questionnaire After each therapy and during weekly follow-up: Global Impression of Change and Patient Preference (Appendix IX: A or B)			X ⁷		X ⁷
Daily Treatment Log and Adverse Assessment (Appendix X)			X		
Individual Patient Dermatome Map-Electrode Placement (Appendix XI) Scrambler only			X		
Audiovisual recordings ^R			X ⁸		
Weekly follow-up patient questionnaire (Appendix XII:A or B)					X ⁹
Written patient summary (if the patient is willing to provide) ^R					X ¹⁰
Research Blood draw for CBC/diff and mRNA ^{11,R}		X		X	
fMRI ^{12,R}		X		X	
Quantitative Sensory Testing ^{13,R}		X		X	

Tests and procedures	Active Monitoring Phase				
	≤30 days prior to registration	Day 1, Prior to therapy	Daily for 14 consecutive days beginning on Day 1 of active therapy	Last day of assigned therapy (±1 day)	Weekly for 8 weeks
Study Coordinator/Nurse phone call to discuss therapy and any concerns, record any adverse events that are reported and to remind the patient to complete questionnaires and mail them			X ¹⁴		X

Footnotes:

1. PS must be done ≤7 days prior to registration.
 2. Appendix II A or B, as labeled depending on neuropathy area type. (This evaluation is used for eligibility.)
 3. For women of childbearing potential only. Must be done prior to first Scrambler therapy (or the first day of the second treatment period, if Scrambler therapy is crossover).
NOTE: This testing is not needed for TENS therapy.
 4. Appendix IV A or B, as labeled depending on neuropathy area to be treated
 5. Beginning on Day 1 of active treatment and continuing for 14 consecutive days, complete Appendix V daily pre/post therapy. If no therapy is received on a day during this timeframe, complete once daily. To be filled out only for primarily treated area. For post-therapy questionnaires VIA and VIB.
 6. Prior to the last therapy.
 7. Appendix IX A or B, as labeled depending on pain or neuropathy area to be treated.
 8. If patient provides written consent for AV recording. Recording may be done on any day.
 9. Appendix XII A or B, as labeled depending on pain or neuropathy area to be treated.
 10. To be completed any time after completion of active treatment.
 11. Optional use in selected patients: Blood draws are completed at Baseline (prior to treatment) and on the last planned day or two of treatment (e.g., Day 9 or 10, if 10 treatments are given but sooner if earlier treatment completion is planned) (±2 days). Ideally, do prior to treatment. See [Section 14.0](#).
 12. fMRI: Optional use in selected patients, do at baseline and on approximately the last day of the initial treatment (±1 day).
 13. Quantitative sensory testing: Optional use in selected patients, do at baseline and then the last day of the initial treatment (±3 days) on 10 patients from each cohort. Do prior to treatment.
 14. For TENS patients only: Study Coordinator or Nurse to call on Treatment Day 2 and once on Treatment Day 8-10 to assess toxicities and remind the patient to complete daily questionnaires and mail them back.
- R Research funded

5.0 Stratification Factors

- 5.1 Gender: Male vs female.
- 5.2 Causative drug: Paclitaxel-regimen vs oxaliplatin-regimen vs other/combination.
- 5.3 Primary problematic area: Upper vs lower extremity.
- 5.4 Primary problematic symptom: Pain vs tingling.

6.0 Registration/Randomization Procedures

6.1 Registration Procedures

- 6.11 To register a patient, access the Mayo Clinic Cancer Center (MCCC) web page and enter the registration/randomization application. The registration/randomization application is available 24 hours a day, 7 days a week. Back up and/or system support contact information is available on the Web site. If unable to access the Web site, call the MCCC Registration Office at (██████████) between the hours of 8 a.m. and 4:30 p.m. Central Time (Monday through Friday).

The instructions for the registration/randomization application are available on the MCCC web page ██████████ and detail the process for completing and confirming patient registration. Prior to initiation of protocol treatment, this process must be completed in its entirety and a MCCC subject ID number must be available as noted in the instructions. It is the responsibility of the individual registering the patient to confirm the process has been successfully completed prior to release of the study agent. Patient registration via the registration/randomization application can be confirmed in any of the following ways:

- Contact the MCCC Registration Office ██████████. If the patient was fully registered, the MCCC Registration Office staff can access the information from the centralized database and confirm the registration.
- Refer to “Instructions for Remote Registration” in section “Finding/Displaying Information about A Registered Subject.”

6.12 Correlative Research

An optional correlative research component is part of this study, there will be an option to select if the patient is to be registered onto this component (see Sections [7.0](#) and [14.0](#)).

- Patient has/has not given permission to give his/her blood sample for research testing
- Patient has/has not given permission to have functional MRI testing (fMRI) for research testing
- Patient has/has not given permission to have Quantitative Sensory Testing (QSART) for research testing
- Patient has/has not given permission to have audiovisual recording for research testing

At the time of registration, the following will be recorded:

- Patient has/has not given permission to store and use his/her sample(s) for future research of cancer at Mayo.
- Patient has/has not given permission to store and use his/her sample(s) for future research to learn, prevent, or treat other health problems.
- Patient has/has not given permission for MCCC to give his/her sample(s) to researchers at other institutions.

